7.2.2 Imaging

State of the art image analysis approaches are applied to process and analyze the acquired brain images and to document individual changes in structural white matter or resting state brain activity. Structural MRI data will be analyzed via voxel based morphometry (VBM) in Statistical Parametric Mapping (SPM). Multiple validated toolboxes will be used (e.g. FreeSurfer, ANTs, CAT12). To correct for distortions caused by the brain tumour itself, Virtual Brain Grafting will be used⁴⁵. DWI images will be processed and analyzed using MRtrix 3.0. Seed-based analysis and independent component analysis (ICA) will be applied to analyze the resting state fMRI data. The association between the obtained MR parameters and the performance on neurocognitive tests will be investigated using (voxel- and region of interest-based) correlation analyses. The independent effects of the predictors (radiation dose, gender, age at treatment, duration of treatment and socioeconomic status) on these neuropsychological test scores and imaging feature values will be analyzed with a (voxel-based) general linear model. For the MR analyses, repeated measures ANOVA will be conducted voxel-based to analyze the within-subject variability in tissue probability maps throughout time (e.g. grey matter or white matter volume, grey matter density, white matter microstructure). The significance threshold will be set at p < 0.05 false discovery rate (FDR) corrected for multiple comparisons.

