Recently developed imaging techniques provide not only an opportunity to estimate and visualise RT-induced damage, but they also offer the opportunity to identify new targets for interventions to prevent or lessen cognitive side-effects. Previous neuroimaging studies only focused on micro-, and macrostructural anatomical changes after RT, including grey¹⁶ and white matter¹⁷ (WM) changes. More recent advanced magnetic resonance imaging (MRI) acquisition and analysis techniques, including diffusion-weighted and functional MRI, are nowadays available. They allow us to probe the underlying structural and functional brain network (i.e. "connectome"), respectively. These techniques might be more sensitive to detect possible therapy-induced structural and functional changes in the brain topology, which could relate to cognitive deficits. Furthermore, cognitive impairment may be driven by damage to specific fibre tracts associated with cognitive assessments, which can be modelled based on diffusion-weighted MRI tractography¹⁸.

The proposed observational cohort study will combine the above-mentioned MR imaging techniques together with elaborate neuropsychological assessments and RT dosimetry in 120

patients who will be examined baseline (before RT) and followed longitudinally after RT. By doing so, we hope to uncover vulnerable brain regions and detect early imaging changes to identify patients at risk. Since neurotoxicity is a complex multifactorial process, the best way to combine these data and make predictions about RT-induced effects is to build so-called normal tissue complication probability (NTCP) models. These mathematical models allow us to estimate the risk of a particular side effect in a structured and validated way for every individual patient. This will enable us to simulate the patient's toxicity risks to spare neurocognitive function in daily life. A previous effect has been conducted by Gondi in 2012, but included a limited number of patients and this model has not been validated to date¹⁹.

In this exploratory prospective study, we thus aim to provide the clinical, radiological and dosimetric data to build a validated NTCP model for neurocognitive decline, which is currently lacking.

3. Trial objectives and Design

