3.1 Trial objectives

The aim of this trial is to study the long-term impact of multimodal treatment (chemotherapy, radiotherapy and surgery) in adult brain and base of skull tumours on neurocognitive functioning using neuropsychological testing combined with advanced MR imaging techniques in a multicenter observational cohort study. We differentiate two main objectives.

The first objective is to build an NTCP model for neurocognitive decline after RT (for each cognitive domain separately), linking dose-volume parameters to structures within the brain susceptible to neurological damage and neurocognitive decline after radiotherapy. These NTCP models will be used to make predictions on neurocognitive decline in future primary brain tumour patients receiving cranial RT. It will provide us with a much needed, evidence-based tool to select the optimal treatment modality for each individual patient and enables us to tailor cranial irradiation towards neurocognition-sparing treatment in the future.

The second objective is to evaluate dose-dependent neurocognitive decline. In particular, we will investigate:

- Prevalence and severity of neurocognitive decline after RT for all cognitive domains
- Brain structures or functional brain connections important in neurocognitive functioning (based on dedicated MRI).
- Dose-dependencies of specific neurocognitive skills after RT in adult brain tumour patients
- Correlations between RT dosimetry and early brain changes (MRI)

With this prospective observational trial, we aim to map the neurocognitive side effects of the irradiation treatment in cranially irradiated patients and the clinical and dosimetrical factors that play a role. Based on these findings, we plan to set up future prospective trials to validate these findings.

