3.3 Secondary endpoints

- Identify early and late changes on structural and functional MR imaging
- Evaluate associations between neurocognitive functioning and RT dosimetry

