3.4 Trial Design

This is an observational cohort study which evaluates primary brain tumour patients longitudinally at the following timepoints: baseline (minimal 4 weeks after surgery (if indicated), before radiotherapy), three months (+/- 2 weeks) after end of radiotherapy, 1 year after end of radiotherapy (+/- 1 month) and 2 years after end of radiotherapy (+/- 1 month). At each visit, neurocognitive testing, a self-report inventory and/or advanced MR imaging will take place. During and after radiotherapy and at each follow-up visit, adverse events will be monitored using CTCAEv5.0²⁰.

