5.2 Neurocognitive assessment

We will perform a standardized neurocognitive test battery in all patients at baseline (prior to RT) and each consecutive year (1 year and 2 years post-RT). The acquisition of neurocognitive assessments takes approximately 1 hour. Results will be followed over time and compared to normative data ^{21,22}.

All these tests and questionnaires have been extensively described and used to quantify neurocognitive functioning in adults. Both neurocognitive testing and completion of the questionnaires takes place in the hospital.

We will use a broad evaluation of neurocognitive performance.

- The Montreal Cognitive Assessment (MOCA), is a screening instrument for cognitive deficits in multiple domains²³.
- Trail Making Task (TMT)²⁴, is an executive task which requires to link characters and digits in the correct sequence.
- Digit span (subtest of the Wechsler Adult Intelligence Scale(WAIS))²⁵ is a working memory task, which requires to repeat digits in same, reversed and sequencing order.
- The Hopkins Verbal Learning Test- Revised (HVLT-R)²⁶ is a verbal memory task for which participants need to repeat 12 words (three repetitions of free-recall) to assess verbal learning. Afterwards, they are asked to repeat or recognize the memorized words (Delayed recall and recognition).
- Controlled Word Association Test (COWAT)²⁷ assesses categoric and phonemic fluency. The participant is required to make verbal associations to a category or different letters of the alphabet by saying all the words which they can think of in this category or beginning with a given letter.
- The Stroop Color and Word Test (SCWT)²⁸ assesses the ability to inhibit cognitive interference that occurs when the processing of a specific stimulus feature impedes the simultaneous processing of a second stimulus attribute.
- The digit symbol substitution test of the WAIS (coding)²⁹ measures processing speed. This test consists of digit-symbol pairs followed by a list of digits. Under each digit the subject

should write down the corresponding symbol as fast as possible. The number of correct symbols within the allowed time is measured.

Cognitive domain	Neurocognitive test	Outcome measurement time				
Attention	TMT B					
Memory	HVLT immediate recall	Sum score - learning				
	HVLT delayed recall	Sum score				
	HVLT recognition	Good recognition-mistakes				
	WAIS IV digit span forward	Total number of series				
Executive functioning	COWAT	Sum of words				

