5.4 MRI imaging

We will perform an advanced MR protocol in every patient. No gadolinium contrast will be administered. Advanced MRI will be performed in all patients prior to RT (baseline), at three months, and at one year post-RT. All subjects will be imaged on the same scanner in each center (UZ Leuven: 3T Philips with a 32-channel phased-array head coil, located in the radiology department at UZ Leuven). Phantom scans will be used to adapt each protocol in every center. Neuroimaging will consist of:

- 3D high-resolution T1-weighted magnetization-prepared rapid acquisition gradientecho (MPRAGE) anatomical scan for grey/white matter volumetry
- o 3D T2-weighted FLAIR to examine leukoencephalopathy
- Advanced diffusion weighted- imaging (DWI). DWI is a technique enabling the visualization and characterization of the WM architecture via the self-diffusion of water molecules allowing us to study potential therapy-induced changes in the WM microstructure. Damage to WM structures for example axonal loss or demyelination may change quantitative DWI parameters such as fractional anisotropy (FA), mean diffusivity (MD) and diffusion kurtosis.
- Resting state functional MRI (rfMRI) to estimate neuronal activity of the brain at rest (examination with eyes closed). rfMRI uses the vascular response nearby electrically active neurons to indirectly visualize brain activity and allows us to determine the functional coherence (or so-called "connectivity") between the different brain regions at rest. Participants will therefore be asked to close their eyes during the examination, but not to fall asleep.
- Susceptibility-weighted MR imaging (SWI) to detect radiation therapy-induced cerebral microbleeds.
- Arterial Spin labeling (ASL) to measure tissue perfusion.

The duration of the proposed scan protocol is maximum 60 minutes.

6. Assessment of Safety

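### The imaging analyses in Section 7.2.2 do not match the early-imaging aims: dose is modelled without the pre-RT scan, change over time without dose or cognition, and early MRI change is never related to later decline

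*Protocol*

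**What the plan says.** **Aims.** Section 3.1 lists, under the second objective, "Correlations between RT dosimetry and early brain changes (MRI"). Section 3.3 makes it a secondary endpoint to "Identify early and late changes on structural and functional MR imaging". Section 2 gives a further purpose for combining imaging, testing and dosimetry: "we hope to uncover vulnerable brain regions and detect early imaging changes to identify patients at risk".

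**Schedule.** Section 5.4: "Advanced MRI will be performed in all patients prior to RT (baseline), at three months, and at one year post-RT". Section 5.2 places the cognitive battery "at baseline (prior to RT) and each consecutive year (1 year and 2 years post-RT"). Section 3.4 shows that the split is deliberate: "At each visit, neurocognitive testing, a self-report inventory and/or advanced MR imaging will take place".

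**Analysis.** Section 7.2.2 names three relevant analyses.

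- MRI and cognition: "The association between the obtained MR parameters and the performance on neurocognitive tests will be investigated using" voxel-based and region-based correlations. Neither the visits to be paired nor the use of levels or changes is stated.
- Dose: a general linear model for test scores and imaging values. The listed predictors are radiation dose, gender, age at treatment, duration of treatment and socioeconomic status.
- Time: a voxel-based repeated measures ANOVA of tissue maps.

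Section 7.2.4 builds the NTCP models from clinical variables and dose. Voxel clusters from the damage heat maps enter only by defining regions whose dose is then used.

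**The concern.** An aim about early change needs an analysis in which the pre-RT scan appears, together with dose for the objective in Section 3.1 or with later cognition for the aim in Section 2. None of the three analyses is specified that way.

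The pre-RT value matters here because dose is planned around the tumour. Tissue near the tumour bed may look abnormal, and cognition may already be reduced, before the first fraction. A post-RT image value regressed on dose, or correlated with a test score, can then reflect tumour and surgery as well as radiotherapy. The listed predictors in 7.2.2 also omit tumour location, which Section 7.2.1 does include for the cognitive scores.

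Two things are at stake. The trial could present as an imaging marker of radiotherapy effect something that was present at baseline. It could also miss a real relation between early MRI change and later decline, because levels carry variation that has nothing to do with change.

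**Working it through.** **1. Schedule**

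| | Baseline | 3 months | 1 year | 2 years |
|---|---|---|---|---|
| MRI | yes | yes | yes | no |
| Cognition | yes | no | yes | yes |

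Baseline-to-3-month MRI change precedes both post-RT cognitive assessments. A lagged analysis is therefore possible with the scheduled data.

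**2. What each stated analysis contains**

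| Analysis in 7.2.2 | Dose | Change from, or adjustment for, pre-RT value | Links MRI to cognition |
|---|---|---|---|
| Correlation | no | not stated | yes, timing not stated |
| General linear model | yes | none listed | no |
| Repeated measures ANOVA | no | yes (within subject) | no |

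No row combines change with dose, and none combines early change with later cognition.

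**3. Plan's own figures.** The protocol gives no sample size or power for the imaging analyses. Its cognitive-change calculation in Section 7.1 reproduces with a paired t-test (d = 0.368 needs 60 patients, d = 1.271 needs 8), but this point does not depend on it.

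**4. Illustration: a level correlation with no post-RT relation.** All inputs except n = 120 are assumed. Let MRI and cognition correlate r0 before RT. Let each have one-year stability s, and let the 1-year values be otherwise unrelated.

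- Implied 1-year correlation: r1 = r0 × s².
- Probability of p < 0.05 (two-sided): Φ(atanh(r1) × √(120 − 3) − 1.96), with √117 = 10.817.

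| r0 | s | r1 | Probability |
|---|---|---|---|
| 0.3 | 0.7 | 0.147 | 36% |
| 0.3 | 0.8 | 0.192 | 56% |
| 0.3 | 0.9 | 0.243 | 76% |
| 0.4 | 0.7 | 0.196 | 57% |
| 0.4 | 0.8 | 0.256 | 81% |
| 0.4 | 0.9 | 0.324 | 95% |

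For r0 = 0.4 and s = 0.8: atanh(0.256) = 0.2618; 0.2618 × 10.817 = 2.832; 2.832 − 1.96 = 0.872; Φ(0.872) = 0.81. A simulation of 10,000 trials at these values gave 81% for the level correlation. Regressing the 1-year score on MRI change and baseline score gave 5%, the nominal rate.

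**5. Illustration: power lost for a true relation.** Assume that early MRI change correlates 0.30 with cognitive change, baseline cognition has SD 1, cognitive change has SD c, and baseline cognition is unrelated to either change. The correlation of MRI change with the 1-year score is then 0.30 × c/√(1 + c²).

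| c | Correlation with 1-year score | Power, n = 120 |
|---|---|---|
| 0.5 | 0.134 | 0.31 |
| 0.75 | 0.180 | 0.50 |
| 1.0 | 0.212 | 0.64 |

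With cognitive change itself as the outcome, the power is 0.92.

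**6. What a lagged analysis could detect.** The smallest correlation detectable with 80% power in one test is tanh((1.96 + 0.842)/√(n − 3)). This gives 0.253 at n = 120, 0.283 at n = 96 and 0.325 at n = 72. At α = 0.01 (Bonferroni for five domains, z = 2.576) the values are 0.306, 0.340 and 0.390. The losses of 20% and 40% are assumptions, since the protocol states no dropout rate.

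**The case against.** A reader might infer that the early-imaging question cannot be answered because no cognitive test accompanies the 3-month scan. The documents do not support that. The objective in Section 3.1 concerns dose and MRI only and needs no cognitive data. For the aim in Section 2, a predictor measured before the outcome is the right order, and the 1- and 2-year tests supply the outcome.

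The strongest defence is that 7.2.2 leaves open whether its variables are levels or changes. The section begins by saying that individual changes will be documented, it plans an analysis of within-subject change, and it plans a correction for distortion by the tumour. Nothing in it excludes change scores. The at-risk aim is a hope expressed in the rationale of a study that calls itself exploratory, not a formal endpoint, and such detail could sit in a statistical analysis plan that is not shown. All of that stands, and it limits the weight of the point.

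It does not remove the point. The protocol is not silent: it names the models and lists the predictors, and those lists omit the pre-RT value. The one analysis that does use change omits dose and cognition. Correcting for distortion makes images analysable; it does not adjust for tissue damage or cognitive loss before RT.

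A reader might also take the 36-95% as this trial's false-positive rate. It is not. The correlations and stabilities are assumed, one uncorrected test is considered where 7.2.2 applies false discovery rate control, and complete data in 120 patients are supposed although discontinued patients are not replaced (Section 4.4). A level correlation of that kind is also real; the error would lie in reading it as a post-RT relation. For that reason multiplicity correction does not remove the problem.

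**Conclusion.** The point holds as a mismatch between aims and stated analyses. As written, 7.2.2 tests dose without change and change without dose, and it relates MRI to cognition without baseline adjustment or lag. This follows from the text and needs no assumption, except that the listed predictors are taken as complete.

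The size cannot be fixed from the documents. Under the assumed values above, a level correlation would be significant in 36-95% of trials with no post-RT relation, and a true change relation of 0.30 would have power of 0.31-0.64 instead of 0.92. These figures show that both errors can be substantial; they do not estimate what will happen in this trial.

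The question is answerable with the scheduled data, and the visit schedule is not at fault. This is an inexpensive improvement to make before analysis, not a defect that invalidates the study.

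**What to change.** In Section 7.2.2:

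- (a) For the objective in Section 3.1, relate 3-month MRI in each region to the dose in that region, with MRI expressed as change from the pre-RT scan or adjusted for it.
- (b) For the at-risk aim in Section 2, regress the 1-year and 2-year cognitive scores, adjusted for baseline score, on baseline-to-3-month MRI change and dose. Name this as the analysis for that aim.
- (c) Keep correlations between MRI and cognitive levels as descriptive, and state which visits are paired.

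The cost is wording and analysis time; no visit, scan or test is added. The downsides are that change measures are noisier than levels and that patients lacking the baseline or 3-month scan drop out of the change analyses, so the number with both scans should be reported.

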7.2.1 Neuropsychological data

The following research questions are addressed by using multiple statistical tests.

- 1. How severe is the neurocognitive decline after treatment and how does it change over time?
- 2. Which neurocognitive domains are affected in which patients?

The first question is addressed by investigating the neurocognitive performance of primary brain and base of skull tumour patients. The performance on neurocognitive measures of the patients will be assessed at 3 timepoints over time. The raw test-scores are converted to normalized zscores based on normative data for each cognitive test. For each cognitive test, cognitive impairment is defined as a z-score \leq 1.5, and patients will be dichotomized according to their impairment status (impaired versus unimpaired). The frequency of impairment will be reported as descriptive information.

We will assess the evolution in the z-scores with a mixed repeated measures model to test changes throughout time. However, if the data are not normally distributed, the Friedman test will be used as alternative approach. The effects of the patient- and treatment-related predictors on the neuropsychological and questionnaire scores will be investigated using general linear models (predictors= tumour location, radiation dose, covariates= gender, age at treatment, time since treatment and socio-economic status) at each timepoint. Bonferroni correction will be applied as

method for statistical correction of multiple tests, for each test outcome (n=5 outcomes; memory, executive functioning, attention, visuomotor function, working memory) that is predicted.

Effect sizes of the tests will be reported. Partial eta squared (hp2) will be computed to estimate effect sizes (weak effect: $np^2 \approx 0.03$; moderate: $np^2 \approx 0.06$; large: $np^2 \geq 0.14$) for linear relationships between predictor and each outcome (e.g. age, time since treatment). Cohen's d will be used to estimate effect sizes for subgroup differences (small effect: 0.2 < d < 0.3; medium: 0.3 < d < 0.8; large: d > 0.8).

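### Sections 7.2.1 and 7.2.2 give two overlapping models, with different covariates and different multiplicity corrections, for the effect of radiation dose on neuropsychological test scores, and nothing says which decides

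*Protocol*

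**What the plan says.** Protocol 7.2.1 (Neuropsychological data) examines effects on the neuropsychological and questionnaire scores with "general linear models (predictors= tumour location, radiation dose, covariates= gender, age at treatment, time since treatment and socio-economic status) at each timepoint". For multiplicity it says "Bonferroni correction will be applied as" the "method for statistical correction of multiple tests, for each test outcome (n=5 outcomes; memory, executive functioning, attention, visuomotor function, working memory) that is predicted".

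Protocol 7.2.2 (Imaging) returns to the same outcomes. It begins "The independent effects of the predictors (radiation dose, gender, age at treatment, duration of treatment and socioeconomic status", closes the bracket, and continues "on these neuropsychological test scores and imaging feature values will be analyzed with a (voxel-based) general linear model". The next sentence concerns images alone: "For the MR analyses, repeated measures ANOVA will be conducted voxel-based to analyze the within-subject variability in tissue probability maps throughout time". The section then ends: "The significance threshold will be set at p < 0.05 false discovery rate (FDR) corrected for multiple comparisons".

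Section 7.2.2 does not list the tests that make up the FDR family. Neither section refers to the other or says which governs dose on test scores. The association between neurocognitive functioning and RT dosimetry is a secondary endpoint in 3.3, and dose-dependency of neurocognitive skills belongs to the second objective in 3.1.

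**The concern.** A reader who wants to know how the plan tests whether radiation dose affects a cognitive score finds two answers. They differ in the adjustment set, so the p-values may differ before any correction, and they differ in the correction applied afterwards.

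The adjustment difference has substance. Tumour location is likely to be related both to the dose a brain region receives and to the function at risk. A dose effect adjusted for location and one not adjusted for it therefore need not agree.

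With both models in the plan and no precedence, a dose-cognition result that fails in one section could be reported from the other without departing from the protocol. The choice could be made after the data are seen. That weakens the correction the protocol chose to apply.

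**Working it through.** **1. The two specifications side by side**

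| | Protocol 7.2.1 | Protocol 7.2.2 |
|---|---|---|
| Outcome | Neuropsychological (and questionnaire) scores | Neuropsychological test scores and imaging feature values |
| Method | General linear model, at each timepoint | General linear model, with voxel-based in brackets |
| Shared terms | Radiation dose, gender, age at treatment, socio-economic status | The same four |
| Terms not shared | Tumour location, time since treatment | Duration of treatment |
| Correction | Bonferroni, five outcomes | FDR at 0.05, family not stated |

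Dose on test score appears in both columns, and no text ranks them.

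**2. The level behind Bonferroni**

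Section 7.2.1 prints no overall alpha. Section 7.1 uses a two-sided 0.05, and its figures reproduce at that level with a paired t-test. For d = 0.368, n = 60 gives power 0.801 (stated 0.800) and n = 120 gives 0.979 (stated 0.979). I take 0.05 as the overall level for 7.2.1 as well:

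- Bonferroni: 0.05 / 5 = 0.01 for each domain.
- Benjamini-Hochberg over the same five (assumed family): the k-th smallest p-value is compared with 0.05 × k / 5, that is 0.01, 0.02, 0.03, 0.04 and 0.05. All p-values up to the largest k that passes are declared.

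**3. Same p-values, both rules (family of five assumed)**

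| p-values | Bonferroni | Benjamini-Hochberg |
|---|---|---|
| 0.012, 0.020, 0.025, 0.035, 0.045 | 0 of 5 (smallest, 0.012, exceeds 0.01) | 5 of 5 (largest, 0.045, is below 0.05) |
| 0.004, 0.018, 0.025, 0.30, 0.60 | 1 of 5 | 3 of 5 (third, 0.025, is below 0.03) |
| 0.02, 0.2, 0.3, 0.5, 0.7 | 0 of 5 | 0 of 5 (0.02 exceeds 0.01; no later one passes) |

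The third row shows that a borderline p-value alone does not produce a conflict. The other four matter.

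**4. How often the rules would part (assumptions stated)**

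In 20,000 simulated data sets per setting, five dose tests were drawn as normal z-values with mean atanh(r) × √(120 − 3 − 5). N = 120 comes from the protocol. The partial correlation r (equal in all five domains) and the between-domain correlation (0 or 0.5) are assumed.

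| Assumed partial r | Chance that at least one domain changes verdict |
|---|---|
| 0 | 0.3% to 1.2% |
| 0.15 | 22% to 25% |
| 0.20 | 42% to 48% |
| 0.25 | 51% to 61% |

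On the same five p-values Benjamini-Hochberg never declared fewer domains than Bonferroni. These figures isolate the correction. They leave out any difference caused by the two covariate sets.

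**5. Other FDR families**

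The smallest p-value must meet 0.05 / m for a family of m tests, unless larger p-values pass at their own ranks.

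- m = 11 (the test measures in the 5.2 table): 0.05 / 11 = 0.0045.
- m = 100,000 voxels (assumed): 0.05 / 100,000 = 0.0000005. The cut-off would reach Bonferroni's 0.01 only if 0.01 / 0.0000005 = 20,000 voxels were declared.

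So the direction of the difference depends on a family that the protocol does not name.

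**The case against.** The strongest reply is that each rule has its own subject. The FDR sentence stands in the imaging section, directly after a sentence confined to the MR analyses, and the model in question is labelled voxel-based. Section 7.2.1 carries the neuropsychological heading and names the five domains. On that reading FDR never touches the test scores. This is plausible and may be what was meant. But the FDR sentence carries no restriction, and the test-score model in the same section has no other threshold. Even on this reading, two dose models with different covariates remain.

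A reader might infer that a borderline dose effect will be positive under one section and negative under the other. The documents do not support that. The outcome depends on the other p-values, on the undefined family and on two non-identical models. The percentages above hold only for an assumed family of five with an equal true effect in every domain; with no effect the rules almost never part.

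A reader might also infer that 7.2.2 is simply the lenient route round a family-wise guarantee. That goes too far as well. With a voxel-sized family FDR could be the stricter rule. Section 7.2.1 corrects over five outcomes only and claims no control across predictors, timepoints or questionnaires.

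Finally, the study calls itself exploratory, the endpoint is secondary, and the NTCP modelling in 7.2.4 uses neither rule. That limits the stakes. An SAP could settle the matter, but the point is a conflict between two protocol statements, not detail left for later.

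**Conclusion.** The point stands in a limited form. Sections 7.2.1 and 7.2.2 specify two overlapping general linear models for dose on neuropsychological test scores, with different covariates and, read literally, different corrections, and neither is given precedence. The same question can therefore receive different answers.

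The overlap and the covariate difference follow from the text alone. The size does not. The contrast of 0 of 5 with 5 of 5 is an illustration, and it rests on FDR being applied over the five domains and on an overall level of 0.05. No single figure for how often verdicts would differ can be drawn from the protocol. The primary endpoints in 3.2 are not affected.

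**What to change.** Add a statement to 7.2.2 with two parts. First, the effect of radiation dose on neuropsychological test scores is tested and judged only by the 7.2.1 model, which includes tumour location, with Bonferroni over the five domains. Second, the FDR threshold covers the imaging analyses only, meaning voxel- or region-based imaging outcomes and the correlations between MR parameters and cognition.

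This is a short text change and needs no new data. Its cost is that some dose-cognition results that FDR would have declared will not be declared.
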